8.1.2 Agent Ordering and Agent Accountability

8.1.2.1 NCI-supplied agents may be requested by eligible participating Investigators (or their

authorized designee) at each participating institution. The CTEP-assigned protocol number must be used for ordering all CTEP-supplied investigational agents. The eligible participating investigators at each participating institution must be registered with CTEP, DCTD through an annual submission of FDA Form 1572 (Statement of Investigator), NCI Biosketch, Agent Shipment Form, and Financial Disclosure Form (FD). If there are several participating investigators at one institution, CTEP-supplied investigational agents for the study should be ordered under the name of one lead participating investigator at that institution.

Confirmation of study patient enrollment onto the study is required for initial drug shipment.

Submit agent requests through the PMB Online Agent Order Processing (OAOP) application. Access to OAOP requires the establishment of a CTEP Identity and Access Management (IAM) account and the maintenance of an “active” account status, a “current” password, and active person registration status. For questions about drug orders, transfers, returns, or accountability, call or email PMB any time. Refer to the PMB’s website for specific policies and guidelines related to agent management.

8.1.2.2 Agent Inventory Records – The investigator, or a responsible party designated by the investigator, must maintain a careful record of the receipt, dispensing and final disposition of all agents received from the PMB using the appropriate NCI Investigational Agent (Drug) Accountability Record (DARF) available on the CTEP forms page. Store and maintain separate NCI Investigational Agent Accountability Records for each agent, strength, formulation and ordering investigator on this protocol.

8.1.3 Investigator Brochure Availability

The current versions of the IBs for the agents will be accessible to site investigators and research staff through the PMB OAOP application. Access to OAOP requires the establishment of a CTEP IAM account and the maintenance of an “active” account status, a “current” password and active person registration status. Questions about IB access may be directed to the PMB IB Coordinator via email.

- Administer infusion solution over at least 60 minutes through an intravenous line containing a sterile, low protein binding, 0.22 micron (or equivalent) in-line filter.
- Do not mix Mogamulizumab with other drugs.
- Do not co-administer other drugs through the same intravenous line.

Patient Care Implications: Refer to the protocol for information on evaluation and management of infusion related reactions.

Agent Ordering: Commercially available from various manufacturers. See package insert for further information.

9. STATISTICAL CONSIDERATIONS

9.1 Study Design/Endpoints

This is a combined phase 1b/2 multicenter, open label, interventional study to evaluate the safety (phase 1b) and efficacy (phase 2) of the combination of Hu5F9-G4 (magrolimab) with mogamulizumab. The phase 1b portion will be a single arm, dose de-escalation 6+3 design to determine a RP2D of Hu5F9-G4 (magrolimab), and will enroll 6-18 patients. A formal amendment is required to proceed to the phase 2 portion of the protocol. The phase 2 portion will be an open label, randomized, two-arm design with for patients with relapsed/refractory MF or SS, randomized 1:1 to either mogamulizumab alone or mogamulizumab plus Hu5F9- G4 (magrolimab), and will enroll 82 patients.

The primary endpoint for the randomized phase 2 portion will be ORR6 – a composite endpoint of both response rate and duration of response. As a historical reference, the ORR6 of the intention-to-treat analysis of mogamulizumab arm of the MAVORIC trial was 21%.

Phase 1b Design Operating Characteristics: The phase 1b 6+3 clinical trial design has the following operating characteristics.

	No Dose	L1	L2	Months to Complete (mean, median, range)	Number of evaluable patients treated (mean, median, range)
True DLT Probability	-	0.1	0.15	-	
Prob MTD 3+3	0.03	0.22	0.75	8.4, 7.6 (3.3-22.1)	6.6, 6 (4-12)
Prob MTD 6+3	0.01	0.13	0.86	6.5, 5.6 (2.0-25.1)	6.9, 6 (5-18)
True DLT Probability	-	0.1	0.3		
Prob MTD 3+3	0.08	0.53	0.39	9.9, 9.5 (3.5-26.2)	8.0, 8.0 (4-12)

NCI Protocol #: 10384

Version Date: September 5, 2023

Prob MTD 6+3	0.03	0.49	0.48	8.6, 8.1 (2.0-25.3)	9.4,9.0 (5-18)
True DLT Probability	-	0.2	0.4		
Prob MTD 3+3	0.32	0.49	0.19	10.2, 9.8 (3.2-26.2)	8.4,8.0 (4-12)
Prob MTD 6+3	0.20	0.55	0.25	9.7, 9.2 (2.1-24.2)	10.8,11.0 (5-18)
True DLT Probability	-	0.3	0.5		
Prob MTD 3+3	0.59	0.33	0.08	9.5, 9.2 (2.5-23.2)	8.0,8.0 (4-12)
Prob MTD 6+3	0.47	0.42	0.10	9.9, 9.5 (2.2-24.3)	11.3, 11 (5-18)

These estimates are based on 800 simulations, and assume a 30% screen failure, and a 20% inevaluable rate (see oneq.netlify.app for simulation engine). The study starts on dose level 2 and only de-escalates if required based on the rules (2 DLTs in the traditional 3+3 design, and 3 DLTs in the 6+3 design). The simulations assume a 10 day mean interarrival time. As the 6+3 design does not de-escalate with 2 DLTs out of 6 patients, it tolerates slightly more toxicity than the traditional 3+3 design. Specifically, a maximum of 2 out of 9 patients with a DLT (or 22.2%) observed toxicity at the MTD is accepted rather than a maximum of 1 out of 6 with a DLT (16.7%) with 3+3 design. These operating characteristics are such that with a 15% DLT rate at the starting dose, the MTD will be selected as that dose with 86% probability, and with a 50% DLT rate at the starting dose, the MTD will be less than that dose with 90% probability. The rules of the 6+3 determine the maximum tolerated dose, but the RP2D may be the MTD or less depending on the severity of the DLTs, sub-DLT level toxicities, later toxicities and clinical judgement. In the phase 2 randomized study, further interim safety analyses are conducted to make sure the observed DLT rate does not exceed 30%.

Phase 2 Power and Sample Size: We anticipate a lower ORR6 response rate for the control mogamulizumab arm of this trial to be lower than that for MAVORIC (Kim *et al*, 2018). This is because mogamulizumab is now FDA-approved and is increasingly being utilized in the treatment of patients with SS in particular, where higher response rates were seen in the MAVORIC trial. Therefore, we anticipate that referrals to this trial will be more skewed towards MF than MAVORIC where Sezary patients comprised 45% of the intention-to-treat (ITT) population. We have therefore estimated that the control arm of this cohort will have an ORR6 of 16% for the purposes of the power calculation, with 30% ORR6 in the SS patients and 10% in the MF patients, who we estimate will comprise 70% of the trial (resulting in a combined ORR6 of 16%). With 82 patients (41 in each arm), and assuming the 2 strata with SS have an ORR6 of 30% and the 2 strata with MF have an ORR6 of 10%, and looking to detect an odds ratio of 3.2 associated with the addition of Hu5F9-G4 (magrolimab), there is 86% power to detect this effect size with 41 patients in each treatment arm, with a type I error (one-sided) of 0.15. The choice of the type I error is based on (Rubinstein *et al.*, 2005). This odds ratio is associated with detecting an improvement from 16% to 36% in the ORR6. This calculation is based on the Mantel-Haenszel (Cochran) test for 2x2 tables for 4 strata (based on MF vs SS and Stage) and calculated with nQuery+nTerim 4.0 (2015).

In addition, if the Sezary patients are more prevalent than we anticipate, reaching a percentage of

patients reflected in the MAVORIC trial (45%), the combined ORR6 is 19% and the power increases from 86% to 88%.

Interim Futility Analysis: A planned interim futility analysis will be performed as per the Wieand rule. When 50% of the patients are evaluable, if the ORR6 of the combination is not superior to the single agent, accrual will hold.

Interim Safety Analysis: Before proceeding to the Phase 2 study, the Phase 1b will report satisfaction of the DLT safety criteria and provide a complete report of adverse events and a listing of patients in the Phase 1b that were taken off treatment due to adverse events, and the cycles in which that occurred. During the Phase 2 study, a formal amendment will be considered if at any point the first course DLT rate exceeds 30%, inclusive of all Phase 1b/2 patients treated at the RP2D on the combination of Hu5F9-G4 (magrolimab) and mogamulizumab, and accrual will be held pending review. Additional toxicity monitoring rules beyond cycle 1 follow:

The grade 3-4 AE rate of mogamulizumab throughout multiple cycles of the MAVORIC study was 41% (75 of 184 patients), with 28/184 stopping for AE (15%). The median PFS was approximately 7.7 months. Two of the three on-treatment deaths with mogamulizumab single agent (sepsis and polymyositis) were considered treatment related (2 of 184).

The optimistic scenario is that the combination of Hu5F9-G4 (magrolimab) and mogamulizumab will have enhanced activity over single agent mogamulizumab offsetting the potential increased toxicity of the doublet over single agent mogamulizumab ab. It is expected that the toxicity will be higher with the doublet, and this will be further amplified if the combination is active, keeping patients on treatment longer and increasing the chance of cumulative toxicities and sporadic toxicities. As a result, the rules for toxicity monitoring throughout the study will trigger a Toxicity Monitoring Committee (TMC) meeting (members of the TMC will receive the report at the time of the trigger and will respond within two weeks of the report of the trigger) to decide upon further action based on the totality of the data on both arms. The Toxicity Monitoring Committee will have the authority to hold study accrual and will send a report to the Data Coordinating Center, which will also be reviewing severe adverse events and the totality of the data at the regularly scheduled intervals (every 6 months) [separate from the monthly data coordination center review of data]. The Toxicity Monitoring Committee will consist of the NCI drug monitor, the NCI disease monitor, the study PI and the site PI/treating physician, or the respective designees for the toxicity committee members.

The triggering rules for Toxicity Monitoring Committee are as follows:

- 1) Any treatment-related death on the combination of Hu5F9-G4 (magrolimab) and mogamulizumab (considered possibly related) will trigger a Toxicity Monitoring Committee meeting. The request for a Toxicity Monitoring Committee meeting will be made within 24 hours of the report of a treatment-related death to the Data Coordinating Center.
- 2) If the reported data documents at least 2 patients and more than 30% of patients stop therapy on the doublet due to adverse events before the third cycle, the Data Coordinating Center (which meets monthly) will trigger a Toxicity Monitoring Committee meeting. If

this rule is triggered, the Toxicity Monitoring Committee can hold accrual or permit continued accrual. If permitting continued accrual, the Toxicity Monitoring Committee will make a recommendation for continuing to monitor the off-treatment pattern after the first time this condition is triggered.

The Data Coordinating Center will compare the rate of AEs meeting DLT criteria (occurring at any point during treatment including outside of the DLT period) on both arms using an alpha-spending function approach with an O'Brien-Fleming monitoring boundary beginning at about 33% of the expected information (28 total patients). The second planned evaluation is at 56 total patients (2/3 information). The Data Coordinating Center will employ a one-sided type I error of 0.15 (spending 0.044 alpha at 28 patients and the remainder at 56 patients). A statistically significant increase in the rate of AEs on the doublet arm by these rules will result in the Data Coordinating Center calling for a Toxicity Monitoring Committee. For example, there is greater than a 70% chance of triggering this review if the cumulative rate of AEs meeting the DLT criteria in the control arm is 41% and the cumulative rate in the doublet arm is 62%. As a further example, this rule will be triggered if the cumulative rate of DLT-level AEs (over all cycles) is 5/14 vs 10/14 for the SOC vs doublet arm and will also be triggered for 11/28 (39%) vs 16/28 (57%) AEs on the respective arms. Once triggered, the Toxicity Monitoring Committee will have the same options as in item 2 above.

Analysis Plan: We will use a stratified Cochran-Mantel-Haenszel χ^2 test to compare between-group differences in ORR6 proportion. The primary analysis will include all patients who begin treatment. Patients who do not have an assessment will be considered treatment failures for the ORR6 endpoint. We will also conduct a secondary analysis on the ITT population (all subjects randomized to a therapy and assigned a study number) and an efficacy evaluable set (all subjects who received the first 12 weeks of treatment and completed the week 12 response assessment).

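### Section 9.1 labels the adverse-event looks at 28 and 56 patients as about 33% and 2/3 information, but its O'Brien-Fleming alpha split fits looks at about half and all of the information

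*Combined protocol and SAP*

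**What the plan says.** The last of the Toxicity Monitoring Committee triggers in Section 9.1 is a between-arm comparison of adverse events that meet DLT criteria at any time on treatment. It uses an alpha-spending approach with an O'Brien-Fleming "monitoring boundary beginning at about 33% of the expected information (28 total patients"). The text continues: "The second planned evaluation is at 56 total patients (2/3 information"). On the error rate: "The Data Coordinating Center will employ a one-sided type I error of 0.15", followed by the split "spending 0.044 alpha at 28 patients and the remainder at 56 patients". No later look is described for this comparison.

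Two worked examples follow. At the first look, "this rule will be triggered if the cumulative rate of DLT-level AEs (over all cycles) is 5/14 vs 10/14" (control vs doublet). At the second, the rule "will also be triggered for 11/28 (39%) vs 16/28 (57%) AEs on the respective arms". The plan also says that "there is greater than a 70% chance of triggering this review if the cumulative rate of AEs meeting the DLT criteria" is 41% on control and 62% on the doublet. The two-proportion test is not named. Sections 9.1 and 9.2 give the phase 2 size as 82 patients, 41 per arm.

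**The concern.** O'Brien-Fleming spending is deliberately sparing early on. An alpha of 0.044 out of 0.15 is a large outlay for one third of the information, and spending the whole of 0.15 at two thirds treats that look as the last one. The named function, the information labels and the alpha split therefore cannot all hold.

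At stake is which trigger is programmed. A statistician who enters the standard function and the labelled fractions into software obtains stricter boundaries than the explicit alphas imply. This is the only formal between-arm toxicity comparison among the triggers, and Section 9.1 itself expects more toxicity on the doublet.

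**Working it through.** **Inputs (Section 9.1; 82 from Sections 9.1 and 9.2).** One-sided alpha 0.15; looks at 14 and 28 per arm; labels 1/3 and 2/3; stated cumulative alpha 0.044 then 0.15; examples 5/14 vs 10/14 and 11/28 vs 16/28; rates 41% vs 62%.

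**Step 1: alpha at the labelled fractions.** The standard one-sided O'Brien-Fleming-type (Lan-DeMets) function is a(t) = 2[1 − Φ(z/√t)], with z = Φ⁻¹(1 − 0.15/2) = 1.4395.

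| t | a(t) |
|---|---|
| 1/3 | 0.0127 |
| 28/82 = 0.341 | 0.0138 |
| 1/2 | 0.0418 |
| 2/3 | 0.078 |
| 56/82 = 0.683 | 0.0815 |
| 1 | 0.15 |

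The stated 0.044 then 0.15 is far from the 1/3 and 2/3 rows and close to the 1/2 and 1 rows. The labels agree with 28/82 and 56/82, which are fractions of planned accrual.

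**Step 2: boundaries.** The first boundary is Φ⁻¹(1 − a₁). The second solves P(Z₁ ≥ c₁ or Z₂ ≥ c₂) = a₂ for a bivariate normal with correlation √(28/56) = 0.707.

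| Alpha used | c₁ | c₂ |
|---|---|---|
| Stated: 0.044, 0.15 | 1.706 | 1.0945 |
| Function at 1/2 and 1 | 1.731 | 1.090 |
| Function at 1/3 and 2/3 | 2.237 | 1.446 |
| Function at 28/82 and 56/82 | 2.204 | 1.423 |

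**Step 3: the plan's examples.** With z = (difference in proportions)/SE:
- 5/14 vs 10/14: the difference is 0.3571. Pooled SE = √(0.5357 × 0.4643 × 2/14) = 0.1885, z = 1.895. Unpooled SE = 0.1760, z = 2.029.
- 11/28 vs 16/28: the difference is 0.1786. Pooled SE = √(0.4821 × 0.5179 × 2/28) = 0.1335, z = 1.337. Unpooled SE = 0.1314, z = 1.359.

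Both cross the stated-split boundaries with either test, so the plan's examples are reproduced. They are also the smallest triggering doublet counts: 9/14 gives 1.512 pooled and 1.578 unpooled, and 15/28 gives 1.072 and 1.083. Neither example crosses 2.237 and 1.446, or 2.204 and 1.423. Against the same control counts, 11/14 (2.291, 2.542) and 17/28 (1.604, 1.642) would then be needed.

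**Step 4: chance of triggering at 41% vs 62%.**

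| Rule | Exact binomial, pooled / unpooled | Normal approximation, pooled / unpooled |
|---|---|---|
| Stated split | 67.1% / 68.2% | 69.5% / 70.8% |
| Function at 1/3 and 2/3 | 55.6% / 55.6% | 55.6% / 57.0% |

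Exact type I error at a common 41% rate is 0.142 pooled and 0.156 unpooled under the stated split. Under the labelled fractions it is about 0.077 with either test.

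**Step 5: another O'Brien-Fleming form.** The plan gives no formula. Half of a two-sided 0.30 function is a(t) = 1 − Φ(1.0364/√t). It gives 0.036 at 1/3 and 0.102 at 2/3, with boundaries 1.795 and 1.356. The first example triggers with either test; the second triggers unpooled (1.359) but not pooled (1.337). This form still does not spend 0.15 at 2/3.

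**The case against.** The strongest reply is that the operative rule is already explicit. Section 9.1 gives the look sizes, the total alpha, the alpha at each look and two examples, all mutually consistent. To go wrong, a programmer would have to pass over the stated spend and not check the examples. This stands in large part: the intended rule can be recovered, and the defect is one of labelling. It does not remove the contradiction, because the labels are called information and sit beside a named spending function.

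The second reply also stands. A reader might infer that any O'Brien-Fleming program run at the labelled fractions contradicts both examples. That holds for the standard one-sided function only. Under the form in Step 5 the first example triggers, and so does the second with unpooled z.

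Third, 0.044 is a rounded figure. Values from 0.0435 to 0.0445 move the second boundary from 1.093 to 1.096. A result such as 9/28 vs 13/28 (pooled z 1.0945) falls inside that range, so the documents do not settle whether it triggers. Nor do they prove that the sponsor took the looks as exactly 1/2 and 1; that is the closest fit and remains an inference.

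Finally, the stakes are low. Crossing only calls the committee, which may let accrual continue. The death trigger ("Any treatment-related death on the combination of Hu5F9-G4 (magrolimab) and mogamulizumab (considered possibly related) will trigger a Toxicity Monitoring Committee meeting"), the early-discontinuation trigger, the 30% first-course DLT hold, the six-monthly review and the DSMB in Section 9.6 all operate separately.

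**Conclusion.** The information labels contradict the alpha split in the same paragraph, and nothing elsewhere in the document resolves it. No O'Brien-Fleming form examined spends the full 0.15 at 2/3 information. The first-look spend is 0.044 against 0.0127 from the standard function, and the cumulative second-look spend is 0.15 against 0.078. For the plan's two control counts, that amounts to one more doublet patient with an event needed at each look, and about 11 to 13 points of exact trigger chance at 41% vs 62%. These sizes assume the standard one-sided function, a two-proportion z test and equal arms of 14 and 28.

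The point is minor. It affects when a review is called; the ORR6 test, the sample size and the other safety triggers are unaffected.

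Two stronger readings are not supported. A reader might conclude that the claimed trigger chance above 70% is wrong. It is only borderline: the normal approximation gives 69.5% to 70.8% and exact enumeration 67% to 68%, and the plan does not say which test or method was used. A reader might also conclude that the alphas should be changed to fit the function. The explicit alphas agree with both examples, so the labels are the part to correct.

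**What to change.** Keep the stated alphas, the two looks and both examples. In Section 9.1:
- Describe 28 and 56 patients as about 33% and 2/3 of the planned accrual of 82, and no longer as information.
- State that for this rule 56 patients is the final look, that 28 is half of its information, and that alpha is fully spent at 56.
- Name the two-proportion test. The examples fit both pooled and unpooled z, so the sponsor must say which was used.
- Print the boundaries computed from the unrounded alpha actually used; with 0.044 taken as exact they are 1.706 and 1.0945.
- Restate the trigger chance at 41% vs 62% for that test and method: exact about 67% pooled and 68% unpooled, or 69.5% and 70.8% by normal approximation.

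Do not replace 0.044 by 0.0418 to match the function at one half. The exact type I error at a common 41% rate would rise from 0.142 to 0.154 pooled and from 0.156 to 0.168 unpooled.

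The cost is a text correction and one named test. Sample size, number of looks and examples do not change.

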9.2 Sample Size/Accrual Rate

Phase 1b: Sample size = 6-18 patients; accrual rate = 4 patients per month

Phase 2: Sample size = 82 patients; accrual rate = 4 patients per month

PLANNED ENROLLMENT REPORT

Racial Categories	DOMESTIC PLANNED ENROLLMENT REPORT (TREATMENT)				Total	
	Ethnic Categories					
	Female	Male	Female	Male		
American Indian/ Alaska Native	0	0	0	0	0	
Asian	3	5	0	0	8	
Native Hawaiian or Other Pacific Islander	4	6	0	0	10	
Black or African American	17	32	5	8	62	
White	2	2	0	0	4	
More Than One Race	1	1	0	0	2	
Total	27	47	5	8	87	

INTERNATIONAL (including Canadian participants) PLANNED ENROLLMENT REPORT (TREATMENT)						
Racial Categories	Ethnic Categories				Total	
	Not Hispanic or Latino		Hispanic or Latino			
	Female	Male	Female	Male		
American Indian/ Alaska Native	0	0	0	0	0	
Asian	0	0	0	0	0	
Native Hawaiian or Other Pacific Islander	0	0	0	0	0	
Black or African American	0	0	0	0	0	
White	0	1	0	0	1	
More Than One Race	0	0	0	0	0	
Total	0	1	0	0	1	

9.3 Stratification Factors

The following stratification factors will be used:

1. Mycosis fungoides *vs* Sezary Syndrome
2. Stage 1B-2A *vs* Stage 2B-IV

9.4 Analysis of Secondary Endpoints

The analysis plan for the secondary objectives will be as follows:

Table 5: Analysis of Secondary Endpoints

Secondary Endpoint	Statistical Method
ORR, ORR4, ORR12	Chi-squared
PFS, DOR, TTNT	Kaplan-Meier method; Log- rank

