Q2W = Every 2 weeks, IV = Intravenous

Phase 2 Design:

The phase 1b portion has been completed and the phase 2 portion of the protocol is now open.. There was one DLT identified in the phase 1b portion of the trial with 6 patients treated at dose Level 1. Therefore, the recommended phase 2 dose (RP2D) was established as **Level 1 (30mg/kg magrolimab starting cycle 1)**. The phase 2 portion will be a two-arm, randomized, open-label design. This cohort will seek to determine whether Hu5F9-G4 (magrolimab) plus

mogamulizumab will have improved efficacy as compared to mogamulizumab alone. We will enroll 82 patients with relapsed or refractory mycosis fungoides (MF) / Sézary Syndrome (SS). Patients will be randomized 1:1 to either Hu5F9-G4 (magrolimab) plus mogamulizumab or mogamulizumab alone. Randomization will be stratified by 2 characteristics: 1) Disease type (MF vs SS) and 2) Stage (1B-2A vs 2B-IV). To encourage accrual and to better assess the added effect of Hu5F9-G4 (magrolimab), the trial will allow for one-way crossover from the mogamulizumab only arm to the combination arm. Crossover will be allowed for patients with progressive disease or stable disease lasting 6 months. While not typically a criterion for crossover in other cancers, prolonged stable disease has not been an acceptable outcome for this patient population due to the presence of symptoms associated with ongoing disease.

TABLE OF CONTENTS

SCHEMA	3
1. OBJECTIVES	9
1.1 Primary Objectives.....	9
1.2 Secondary Objectives.....	9
1.3 Exploratory Objectives	9
2. BACKGROUND	9
2.1 Study Diseases	9
2.2 CTEP IND Agent.....	11
2.3 Other Agent.....	15
2.4 Rationale	16
2.5 Correlative Studies Background	20
3. PATIENT SELECTION	24
3.1 Eligibility Criteria	24
3.2 Exclusion Criteria	26
3.3 Inclusion of Women and Minorities	28
4. REGISTRATION PROCEDURES	28
4.1 Investigator and Research Associate Registration with CTEP	28
4.2 Site Registration.....	29
4.3 Patient Registration.....	32
4.4 General Guidelines.....	34
5. BIOMARKER, CORRELATIVE, AND SPECIAL STUDIES	34
5.1 Summary Table for Specimen Collection.....	34
5.2 Specimen Procurement Kits and Scheduling.....	36
5.3 Specimen Tracking System Instructions.....	36
5.4 Specimen Collection	40
5.5 Shipping Specimens from Clinical Site to the EET Biobank	42
5.6 Biomarker Plan	45
5.7 Integrated Correlative Studies.....	51
5.8 Exploratory/Ancillary Correlative Studies	51
6. TREATMENT PLAN	55
6.1 Agent Administration.....	55

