12.2 Definitions of Study Endpoints

Overall Response Rate (ORR): ORR is defined as the proportion of patients who have a partial or complete response to therapy as defined by the global response score.

Duration of Response (DOR): DOR is defined as the duration of overall response is measured from the time measurement criteria are met for CR or PR (whichever is first recorded) until the first date that recurrence or PD is objectively documented.

Overall Response Rate 4 (ORR4): ORR4 is defined as the proportion of patients who have a partial or complete response to therapy AND a duration of response \geq 4 months.

Overall Response Rate 6 (ORR6): ORR6 is defined as the proportion of patients who have a partial or complete response to therapy AND a duration of response \geq 6 months.

Overall Response Rate 12 (ORR12): ORR12 is defined as the proportion of patients who have a partial or complete response to therapy AND a duration of response \geq 12 months.

Progression-Free Survival (PFS): PFS is defined as the duration of time from start of treatment to time of progression or death, whichever occurs first.

Time to next treatment (TTNT): TTNT is defined as the duration of time from the start of treatment on this protocol to time of the next anti-neoplastic therapy.

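### Table 5 could name for ORR, ORR4 and ORR12 the same stratified Cochran-Mantel-Haenszel test as for ORR6: a cheap, low-priority improvement, not an error

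*Combined protocol and SAP*

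**What the plan says.** Section 9.3 introduces the two factors with "The following stratification factors will be used" and lists MF against SS, and stage 1B-2A against 2B-IV. The Phase 2 Design text in the Schema gives the same two factors for the randomisation.

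For the primary endpoint, the Analysis Plan in Section 9.1 is explicit: "We will use a stratified Cochran-Mantel-Haenszel". The power paragraph matches it: "This calculation is based on the Mantel-Haenszel (Cochran) test for 2x2 tables for 4 strata". That paragraph also treats disease type as prognostic, "with 30% ORR6 in the SS patients and 10% in the MF patients".

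Table 5 in Section 9.4 has two rows. One pairs "ORR, ORR4, ORR12" with a chi-squared test. The other pairs PFS, DOR and TTNT with "Kaplan-Meier method; Log- rank". Neither row mentions strata, and nothing elsewhere in the document says that the secondary tests use them. Table 5 states no alpha and no power.

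Section 12.2 gives the definition "ORR4 is defined as the proportion of patients who have a partial or complete response to therapy AND a duration of response" of at least 4 months. ORR6 and ORR12 are worded alike, with 6 and 12 months.

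**The concern.** ORR4, ORR6 and ORR12 are one endpoint at three cut-offs. Read literally, the plan gives the middle one a test that respects the randomisation strata and the outer two a test that ignores them, without giving a reason. Two analysts working from Table 5 could produce different p-values for ORR4.

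When strata are prognostic and randomisation is balanced within them, an unstratified test tends to be somewhat conservative. The plan itself assumes a threefold difference in ORR6 between SS and MF. What is at stake is a little power and a little analyst discretion on secondary endpoints.

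**Working it through.** **Inputs from Section 9.1:** 82 patients, 41 per arm; odds ratio 3.2; control ORR6 30% in SS and 10% in MF; SS 30% of patients (45% in the plan's alternative); one-sided alpha 0.15. **Assumptions:** stage splits 50:50 within disease type and has no effect on response; alpha 0.15 is borrowed for the secondary endpoints; no continuity correction.

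**1. Reproduce the plan's figure.** The treated rate is q = 3.2p/(1 − p + 3.2p).
- SS: 0.96/1.66 = 0.578. MF: 0.32/1.22 = 0.262.
- Overall: control 0.3×0.30 + 0.7×0.10 = 0.16; treated 0.3×0.578 + 0.7×0.262 = 0.357. The plan says 16% to 36%.

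Patients per arm are 6.15 in each of the two SS strata and 14.35 in each of the two MF strata. With p̄ = (p+q)/2 in each stratum:
- Effect: Σ(n/2)(q − p) = 6.15×0.278 + 14.35×0.162 = 4.04
- Null variance: Σ(n/2)p̄(1 − p̄) = 6.15×0.246 + 14.35×0.148 = 3.64
- Alternative variance: Σ(n/4)[p(1 − p) + q(1 − q)] = 3.075×0.454 + 7.175×0.2835 = 3.43
- CMH power: Φ((4.04 − 1.036×√3.64)/√3.43) = Φ(1.11) = 86.7%. The plan states 86%. At 45% SS the formula gives 88.8%; the plan states 88%.

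The unstratified chi-squared formula on the same inputs has pooled SE √(2×0.2586×0.7414/41) = 0.0967 and unpooled SE √((0.1344 + 0.2296)/41) = 0.0942. Power is Φ((0.197 − 1.036×0.0967)/0.0942) = Φ(1.03) = 84.8%.

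**2. Simulate both tests.** These runs use permuted blocks of 4 within the four strata and 400,000 trials per setting. Only the first row uses rates from the plan. The 37/21 row is chosen so that 0.45×37% + 0.55×21% = 28.2%, close to the 28% ORR cited in Section 2.3.1. The other rows are assumptions.

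| Control rate SS/MF | Size at 30% SS, unstratified / CMH | Power at 30% SS | Power at 45% SS |
|---|---|---|---|
| 30/10 (ORR6) | 0.148 / 0.152 | 86.0 / 87.0 | 88.0 / 89.0 |
| 37/21 (ORR-like) | 0.147 / 0.151 | 92.8 / 92.9 | 93.2 / 93.3 |
| 45/21 (ORR-like) | 0.143 / 0.151 | 92.5 / 92.7 | 92.8 / 92.9 |
| 35/13 (ORR4-like) | 0.146 / 0.153 | 88.8 / 89.6 | 90.1 / 90.8 |
| 15/5 (ORR12-like) | 0.152 / 0.155 | 76.1 / 76.3 | 79.2 / 79.6 |
| 40/5 (strong contrast) | 0.131 / 0.152 | 75.4 / 80.3 | 80.3 / 84.7 |
| 28/28 (no difference) | 0.150 / 0.151 | 94.1 / 94.0 | not run |

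**3. Source of the gain.** If each test is held to its own exact 15% null cut-off, power at the ORR6 rates with 30% SS is 86.8% for both. The gain there is recovered test size. At 15/5 the unstratified test is already at 0.152, so it is not conservative, and CMH is slightly further above nominal.

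**4. Sensitivity to set-up.** If stratum sizes are fixed instead, the ORR6 comparison moves with the exact split: one split gave 83.9 against 87.3, another 87.3 against 87.3. The permuted-block figures average over such splits.

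**5. A stricter alpha.** At an assumed one-sided 0.025 with 30% SS, unstratified against CMH power is 54.1 / 56.9 (30/10), 70.0 / 69.8 (37/21), 59.5 / 62.0 (35/13), 39.2 / 39.8 (15/5) and 74.0 / 72.4 (28/28). The last is the downside: about 1.7 points, or 1.6 from these rounded figures.

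**6. Log-rank.** This takes the control median of 7.7 months (Section 2.3.1) and accrual of 4 per month (Section 9.2). It assumes 12 months of follow-up after last entry and a hazard ratio of 0.65, giving about 64 events with no stratum effect. Unstratified against stratified power at one-sided 0.15 is 75.1 / 73.5 in one run and 75.2 / 73.3 in another with no stratum effect. It is 72.4 / 73.3 at an assumed stage hazard ratio of 2, and 67.0 / 72.7 at 3. TTNT was not simulated separately.

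**The case against.** The strongest reply is that nothing is wrong. A stratified primary test beside unstratified secondary tests is a legitimate choice, and Table 5 makes no power or success claim that could fail. That stands, and it is why this is only an improvement.

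A second reply is that Table 5 never says unstratified. It is two lines of shorthand, and a CMH test is itself a chi-squared test. That also stands: the unstratified reading comes from silence, in contrast with the explicit wording for ORR6. The silence still leaves the choice open.

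A third reply is that the gain is close to nil and rests on assumed rates and a borrowed alpha. This is right about size. The case for the change is consistency between sibling endpoints at almost no cost, with power secondary.

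A fourth reply is that for the log-rank test the change can lose power. That stands too. Section 2.1.1 lists overall clinical stage among the main prognostic factors, but the documents give no stage or disease-type hazard ratio for PFS or TTNT. Stratifying that test is therefore a trade-off.

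**Conclusion.** The point holds as a low-priority consistency improvement for ORR, ORR4 and ORR12. At one-sided 0.15 the expected gain is about 0 to 1 power point at plausible rates, mostly recovered test size where the unstratified test is conservative. A gain of 4 to 5 points needs a contrast like 40% against 5%, which the documents nowhere suggest. If the strata are not prognostic, the cost is about 0.1 point at one-sided 0.15 or about 1.7 points at one-sided 0.025. These sizes rest on the assumed stratum rates, the equal stage split with no stage effect, and the borrowed alpha.

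A reader might infer three stronger things that the documents do not support:
- That the secondary tests are invalid or inflate type I error. In the table the unstratified test runs from 0.131 to 0.152 against 0.15, and where it is highest CMH is no closer to nominal.
- That the 86% power or the primary comparison is affected. Both already use the stratified test.
- That PFS and TTNT clearly lose power unless stratified. With no stratum effect the stratified log-rank test loses about 1.5 to 2 points; it gains only if stage is clearly prognostic.

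DOR is measured only from the time a response is reached (Section 12.2), so it exists among responders alone and lies outside this point.

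**What to change.** In Table 5, replace the chi-squared entry for ORR, ORR4 and ORR12 with the CMH test stratified by disease type and stage, handled exactly as for ORR6. Do not add a sparse-stratum rule for these endpoints alone: Section 9.1 has none for ORR6, so that would recreate the mismatch.

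Optionally, for consistency with the randomisation, name a log-rank test stratified by the same factors for PFS and TTNT, accepting the trade-off and claiming no power gain. DOR shares that row, so it would then need a row of its own, unchanged.

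The cost is a wording change in one table. It needs no extra data, patients or visits. The only statistical cost is the small possible power loss given above.
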